### **7.1.6 Dose Discontinuation Criteria (Nivolumab)**

Nivolumab treatment should be permanently discontinued for the following:

- Any Grade 2 study treatment-related uveitis or eye pain or blurred vision that does not respond to topical therapy and does not improve to Grade 1 severity within the re-treatment period OR requires systemic treatment
- Any Grade 3 non-skin, study treatment-related AE lasting > 7 days or recurs, with the following exceptions for laboratory abnormalities, study treatment-related uveitis, pneumonitis, bronchospasm, hypersensitivity reactions, infusion reactions, and endocrinopathies:
  - Grade 3 study treatment-related uveitis, pneumonitis, bronchospasm, neurologic toxicity, myocarditis, hypersensitivity reaction, or infusion reaction of any duration require discontinuation
  - Grade 3 study treatment-related endocrinopathies adequately controlled with only physiologic hormone replacement do not require discontinuation. Adrenal insufficiency requires discontinuation regardless of control with hormone replacement.
  - Grade 3 study treatment-related laboratory abnormalities do not require treatment discontinuation except:
    - Grade 3 study treatment-related thrombocytopenia > 7 days or associated with clinically significant bleeding requires discontinuation\*
    - AST or ALT > 8 x ULN or Total Bilirubin > 5 x ULN requires discontinuation
    - Concurrent AST or ALT > 3 x ULN and Total Bilirubin > 2 x ULN

\* In most cases of Grade 3 AST or ALT elevation, study treatment(s) will be permanently discontinued. If the investigator determines a possible favorable benefit/risk ratio that warrants continuation of study treatment(s), a discussion between the investigator and the BMS Medical Monitor/designee must occur.

- Any Grade 4 study treatment-related adverse event or laboratory abnormality (including but not limited to creatinine, AST, ALT, or TBili), except for the following events which do not require discontinuation
  - Grade 4 neutropenia  $\leq 7$  days
  - Grade 4 lymphopenia or leukopenia
  - Isolated Grade 4 amylase or lipase abnormalities that are not associated with symptoms or clinical manifestations of pancreatitis. Consult Medical Monitor for Grade 4 amylase and lipase abnormalities
  - Isolated Grade 4 electrolyte imbalances/abnormalities that are not associated with clinical sequelae and are corrected with supplementation/appropriate management within 72 hours of their onset
  - Grade 4 study treatment-related endocrinopathy AEs such as adrenal insufficiency, ACTH (adrenocorticotropic hormone) deficiency, hyper- or hypothyroidosis, or glucose intolerance, which resolve or are adequately controlled with physiologic hormone replacement (steroids, thyroid hormones) or glucose controlling agents, respectively, may not require discontinuation after discussion with and approval from the BMS Medical Monitor.
- If dosing is withheld for  $> 6$  weeks from the previous dose with the following exceptions:
  - Dosing withholdings to allow for prolonged steroid tapers to manage study treatment-related adverse events are allowed. Prior to re-initiating study treatment in a participant with dose omissions lasting  $> 6$  weeks, the BMS medical monitor must be consulted. Tumor assessments should continue as per protocol even if dosing is withheld.
  - Dosing withholdings  $> 6$  weeks that occur for non-study treatment-related reasons may be allowed if approved by the BMS medical monitor. Prior to re-initiating study treatment in a participant with dose omissions lasting  $> 6$  weeks, the BMS medical monitor must be consulted. Tumor assessments should continue as per protocol even if dosing is withheld.
- Any adverse event, laboratory abnormality, or intercurrent illness which, in the judgment of the Investigator, presents a substantial clinical risk to the participant with continued dosing
- Disease progression as determined by investigator assessment following the guidelines given by the Lugano 2014 Classification
- Participant who initiated the preparative regimen for allogeneic stem cell transplant (allogeneic SCT) or ASCT after the first dose of study treatment
- Initiation of antineoplastic therapy (ie, chemotherapy, hormonal therapy, immunotherapy, radiation therapy except for palliative radiation therapy, or standard or investigational agents for treatment of cancer)

### **7.1.7 Dose Discontinuation Criteria (Brentuximab Vedotin)**

Brentuximab vedotin treatment should be permanently discontinued for reasons provided in [Table 7.4.2-1](#). Dose delays of more than 3 weeks may be allowed after discussion with the study medical monitor.

### **7.1.8 Dose Delay Criteria (Nivolumab and Brentuximab Vedotin)**

If the nivolumab dose is delayed, treatment can be continued with BV. Similarly, if the BV dose is delayed, treatment can be continued with nivolumab. See Section 7.4 for instructions concerning dosage modifications.

## **7.2 Method of Treatment Assignment**

All participants will be centrally randomized using an Interactive Response Technology (IRT). Before the study is initiated, each user will receive log-in information and directions on how to access the IRT. After the participant's initial eligibility is established and informed consent has been obtained, the participant must be enrolled into the study by calling an IRT and be assigned a participant number. Specific instructions for using IRT will be provided to the investigational site in the IRT manual. The randomization procedures will be carried out via permuted blocks within each stratum. Stratification will be performed on two factors: 1) Prior ASCT status (YES/NO). 2) Prior BV use (YES/NO).

Once registered, participants who have signed the ICF and met all eligibility criteria will be ready to be randomized. The following information is required for participant randomization:

- Participant number
- Date of birth
- Prior therapies and types of therapy (chemotherapy, ASCT)

Study treatment will be dispensed at the study visits as listed in Schedule of Activities ([Section 2](#)).

## **7.3 Blinding**

This is an open-label study, blinding procedures are not applicable.

## **7.4 Dosage Modification**

The BMS medical monitor should be contacted when any dose is reduced, regardless of the causality.

### **7.4.1 Nivolumab**

Dose reductions and escalations of nivolumab are not permitted.

### **7.4.2 Brentuximab vedotin**

The recommended dose modifications for BV treatment associated toxicity are provided in [Table 7.4.2-1](#). Doses reduced for BV-related toxicity should not be re-escalated without discussion with the sponsor. Dose escalation of BV beyond 1.8 mg/kg is not permitted. Dose reductions below 1.2 mg/kg are not allowed.

If BV treatment is delayed for any reason, other treatments must be continued. Participants who require delay of BV should be re-evaluated frequently and BV dosing resumed when re-treatment criteria are met. Dose delays of more than 3 weeks may be allowed after discussion with the study medical monitor.

Recommendations for management of infusion related reactions due to BV are described in [Section 7.1.5](#).

Participants who discontinue nivolumab treatment due to a treatment-related AE may continue treatment with BV for a maximum of 16 cycles, or until disease progression or unacceptable toxicity, whichever occurs first. Participants who discontinue BV due to a treatment-related AE may continue to receive nivolumab treatment until disease progression or unacceptable toxicity.

**Table 7.4.2-1: Dose Modifications for Brentuximab Vedotin**

Toxicity	Grade 1	Grade 2	Grade 3	Grade 4
Peripheral Neuropathy	Continue at same dose level	Hold until peripheral neuropathy resolves to $\leq$ Grade 1 and then resume treatment at 1.2 mg/kg a	Withhold (delay) until toxicity resolves to $\leq$ Grade 2 or baseline, then resume treatment at 1.2 mg/kg or discontinue if reduction has already occurred.	Discontinue treatment
Non-hematologic (except peripheral neuropathy)	Continue at same dose level	Continue at same dose level	Withhold (delay) dose until toxicity is $\leq$ Grade 2 or has returned to baseline, then resume treatment at the same dose level b	Withhold dose until toxicity is $\leq$ Grade 2 or has returned to baseline, then reduce dose to 1.2 mg/kg and resume treatment, or discontinue at the discretion of the investigator a,b,c
Hematologic d	Continue at same dose level	Continue at same dose level	Withhold (delay) until toxicity resolves to $\leq$ Grade 2 or baseline, then resume treatment at the same dose level. c Growth factor support (G-CSF or GM-CSF) should be considered for subsequent cycles. If Grade 4 neutropenia recurs despite growth factor support, consider discontinuation.	Discontinue treatment

a Dose reductions below 1.2 mg/kg are not allowed, and toxicities should be managed with dose delays

b Participants who develop Grade 3 or 4 electrolyte laboratory abnormalities may continue study treatment without dose delay

c Treatment should be discontinued for participants who experience Grade 4 infusion-related reactions.

d Support with blood product transfusions allowed per institutional standard of care.

e Participants who develop Grade 3 or 4 lymphopenia may continue study treatment without dose delay.

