## 7.1 Treatments Administered

Infusions will be performed over a period of once every 3 weeks. Participants should begin study treatment within 3 calendar days of randomization. Participants will be monitored continuously for AEs while on study. Study treatment modifications (eg, dose delay or discontinuation) will be based on specific laboratory and AE criteria (Section 7.4). Doses of study treatment may be interrupted, withheld, or discontinued depending on how well the participant tolerates the study treatment. Treatment with nivolumab will be continued as described in Section 5.1 until disease progression or unacceptable toxicity. Participants treated with nivolumab who achieve a CR may discontinue treatment after a maximum of 2 years of therapy, provided that there is no prohibitive toxicity. Administration of BV should be discontinued after a maximum of 16 cycles, or until disease progression or unacceptable toxicity, whichever occurs first.

All participants who discontinue therapy will be followed through Safety Follow-up Visit 2.

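### Table 7.4.2-1 has no combined AST/ALT and bilirubin limit for BV, so a Grade 2 pattern that permanently stops nivolumab falls in a cell that keeps BV at the same dose

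*Protocol*

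**What the plan says.** Section 7.1 says that changes to study treatment "will be based on specific laboratory and AE criteria (Section 7.4"). For BV, Section 7.1.7 sends permanent stops to Table 7.4.2-1, and Section 7.4.2 calls the table's entries recommended.

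The table has three rows: peripheral neuropathy, other non-hematologic toxicity, and hematologic toxicity. It has no hepatic row, no ULN value and no liver footnote. In the non-hematologic row:

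- Grade 2: "Continue at same dose level".
- Grade 3: withhold until toxicity is at or below "Grade 2 or has returned to baseline, then resume treatment at the same dose level".
- Grade 4: withhold until toxicity is at or below "Grade 2 or has returned to baseline, then reduce dose to 1.2 mg/kg and resume treatment", or stop at the investigator's discretion.

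The two footnotes on laboratory abnormalities both relax the rules: "Participants who develop Grade 3 or 4 electrolyte laboratory abnormalities may continue study treatment without dose delay" (footnote b) and "Participants who develop Grade 3 or 4 lymphopenia may continue study treatment without dose delay" (footnote e).

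Nivolumab has explicit liver rules. Section 7.1.1 delays it for drug-related Grade 2 AST, ALT or bilirubin. Section 7.1.2 lets it resume only once the values are back to baseline. Section 7.1.6 stops it permanently when AST or ALT exceeds 3 x ULN together with total bilirubin above 2 x ULN. The third bullet of Section 7.1.2 says that combined Grade 2 values can meet that rule, and that *study treatment* should then be stopped for good.

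**The concern.** Every treated participant is assigned BV, and Section 3.3 lists hepatotoxicity among BV's less common notable events. The AST/ALT and bilirubin limits that end nivolumab are also the numeric part of the potential drug-induced liver injury (DILI) definition in Section 9.2.7. That definition further requires no initial cholestasis and no other apparent cause. Section 9.2.7 requires such cases to be reported as SAEs but attaches no BV dosing action.

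This is more than missing detail, because a printed rule covers these values and points towards continued dosing. In the BV-alone arm no nivolumab rule would prompt anyone to stop. A site relying on the table alone would give the next BV dose at the current level, up to 1.8 mg/kg.

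**Working it through.** The documents give no figure to reproduce and no arithmetic applies. The check sets every visible liver-related dosing rule for the two drugs side by side. The Grade 2 mapping comes from Section 7.1.2 itself, not from outside grading tables.

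| Treatment-related liver values | Nivolumab | BV (Table 7.4.2-1) |
|---|---|---|
| Grade 2, combined limits not met | Delay (7.1.1); resume at baseline (7.1.2) | Continue, same dose |
| Grade 2, AST or ALT > 3 x ULN and bilirubin > 2 x ULN | Permanent stop (7.1.2, 7.1.6) | Continue, same dose |
| Grade 3 | Stop per 7.1.1; 7.1.6 allows a discussed exception for AST/ALT | Hold to Grade 2 or lower, or baseline; then same dose |
| Grade 4 | Permanent stop (7.1.6) | Hold to Grade 2 or lower, or baseline; then 1.2 mg/kg, or stop |

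**BV-alone arm.** Only the last column applies. The second row is the gap at first occurrence. The third and fourth rows create the same gap at restart: the test for resuming BV is Grade 2 or lower, and Section 7.1.2 shows that Grade 2 values can still exceed both limits.

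**Combination arm.**
- If the toxicity is attributed to nivolumab, Section 7.1.1 lets BV continue, and Section 7.4.2 allows up to 16 cycles after nivolumab stops for a related event.
- If it is attributed to BV, the table's Grade 2 cell applies and BV again continues.
- Against both, the third bullet of Section 7.1.2 stops *study treatment*, which Section 7 says comprises nivolumab and BV. Read literally, that stops BV as well.
- The heading of Section 7.1.2 names nivolumab only, and Section 7.1.7 ties BV stops to the table. The narrower reading is therefore the better one, but the text is in conflict.

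**General safeguards, checked for a BV liver value.**
- Section 7.1: "Administration of BV should be discontinued after a maximum of 16 cycles, or until disease progression or unacceptable toxicity, whichever occurs first". Unacceptable toxicity is not given a liver value.
- Section 8.1: a mandatory stop, triggered by the investigator's opinion of a laboratory abnormality or event.
- Section 9, opening list: immediate safety concerns must go to the sponsor at once, to decide whether treatment continues.
- Section 9.4.4: chemistry results must be reviewed before each dose.
- Section 9.2.7 and Appendix 3: potential DILI is an important medical event, reported as an SAE within 24 hours.
- Section 5.1.1: medical-monitor and sponsor safety review can modify the regimen.

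None of these states an AST, ALT or bilirubin value at which BV is held or stopped.

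**The case against.** The strongest reply is that a site would not simply give the next dose. Section 9 requires a sponsor discussion that ends in a decision to continue or discontinue. It applies to any drug and either arm, and a DILI-pattern result is hard to see as anything but an immediate safety concern. Section 8.1 and the pre-dose laboratory review add to this. That stands, and it lowers the practical risk. It does not remove the contradiction between the printed cell and those general duties, and it leaves the trigger to individual judgment.

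Two further points stand in full. Different drugs may reasonably carry different limits, so nivolumab's permanent stop need not be copied to BV. And the absence can be claimed only for visible text: Section 7.1.3 is redacted, the hepatic algorithm in Appendix 5 is a figure that is not shown, and the BV label that the protocol points to is not available here. Appendix 5 covers immuno-oncology agents and regimens, so it might reach BV within the combination. Nothing visible extends it to BV alone.

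A reader might infer more than the documents support:
- **That BV has no liver rule at all.** It does: the non-hematologic row holds BV at Grade 3, and at Grade 4 requires a hold and dose reduction or allows a stop.
- **That the protocol makes sites continue BV in both arms.** It does not. The table is a recommendation, the safeguards override it, and Section 7.1.2 read literally stops BV in the combination arm.
- **That potential DILI has no dosing consequence.** Section 9.2.7 alone has none, but Section 9 requires the sponsor-level decision.

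**Conclusion.** The point holds in a limited form. In the visible text, BV liver toxicity is governed only by generic grades. The combined Grade 2 pattern therefore falls under continued dosing, and a restart after a Grade 3 or 4 hold is allowed with both limits still exceeded. This is clear for the BV-alone arm. For the combination arm the finding is a conflict between Section 7.1.2 and the table, not a settled rule that BV continues.

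The size is low. Enrollment closed with 23 participants randomized, and the documents give neither the rate of this liver pattern nor the number still on BV, so no case count or exposure figure can be given. This is a cheap patient-safety improvement. It does not bear on the validity of the trial's results.

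The conclusion assumes that neither Section 7.1.3 nor the hepatic figure in Appendix 5 sets a BV limit. If either does, the remaining task is to make the table agree with it.

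**What to change.** Add a footnote to the non-hematologic row of Table 7.4.2-1, applying to both arms:

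- Withhold BV when AST or ALT > 3 x ULN occurs with total bilirubin > 2 x ULN, pending evaluation against Section 9.2.7 and the sponsor discussion required in Section 9.
- Do not resume BV, including after a Grade 3 or 4 hold, while both limits are exceeded.
- Use a baseline-adjusted bilirubin limit for participants with Gilbert Syndrome, whom Section 6.1 admits with total bilirubin below 3.0 mg/dL.

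The sponsor's clinical team should decide whether and when the hold becomes a permanent stop.

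Do not narrow *study treatment* to nivolumab in Section 7.1.2 or 7.1.6 unless this footnote is in place. The wording in Section 7.1.2 is the only visible text that could stop BV at exactly these values.

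The cost is one footnote. No tests are added: Table 2-2 already has AST, ALT, ALP and bilirubin drawn within 72 hours before dosing, and Section 9.4.4 requires their review first. The downside is a few more BV holds.

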### 2) Medical History and Concurrent Diseases

- a) Participants with known history of pancreatitis or progressive multifocal leukoencephalopathy (PML)
- b) Participants with active interstitial pneumonitis or CT evidence of  $\geq$  Grade 1 pneumonitis.
  - i) If the participant has a history of interstitial pneumonitis, they must have CT evidence of resolution.
- c) Participants with neuropathy  $\geq$  Grade 2, infection  $\geq$  Grade 3, or documented history of coronary artery disease, cardiovascular accidents, or congestive heart failure (CHF) class III/IV.
- d) Any serious or uncontrolled medical disorder that, in the opinion of the investigator, may increase the risk associated with study participation or study treatment administration, impair the ability of the participant to receive protocol therapy, or interfere with the interpretation of study results
- e) Prior malignancies (other than HL) are excluded unless a complete remission was achieved at least 3 years prior to study entry and no additional therapy is required or anticipated to be required during the study period (exceptions include, but are not limited to, non-melanoma skin cancers; in situ bladder cancer, in situ gastric cancer, or in situ colon cancers; in situ cervical cancers/dysplasia; in situ carcinoma of the prostate; or breast carcinoma in situ).
- f) Participants with an active, known or suspected autoimmune disease. Participants with type I diabetes mellitus, hypothyroidism only requiring hormone replacement, skin disorders (such as vitiligo, psoriasis, or alopecia) not requiring systemic treatment, or conditions not expected to recur in the absence of an external trigger are permitted to enroll. For any cases of uncertainty, it is recommended that a BMS medical monitor be consulted prior to signing informed consent.
- g) Participants with a condition requiring systemic treatment with either corticosteroids ( $> 10$  mg daily prednisone equivalents) or other immunosuppressive medications within 14 days of study treatment administration. Inhaled or topical steroids, and adrenal replacement doses 10mg daily are permitted in the absence of active autoimmune disease.
- h) Evidence of active brain metastases on brain imaging (ie, MRI or contrast CT).

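### For BV peripheral neuropathy, the restart threshold is looser after a Grade 3 event than after a Grade 2 event

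*Protocol*

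**What the plan says.** Protocol Section 7.1.7 and Section 7.4.2 both refer to Table 7.4.2-1 for BV dose changes. Its peripheral neuropathy row reads as follows.

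- **Grade 1:** BV continues unchanged.
- **Grade 2:** BV is held until neuropathy is at or below "Grade 1 and then resume treatment at 1.2 mg/kg".
- **Grade 3:** BV is withheld until toxicity is at or below "Grade 2 or baseline, then resume treatment at 1.2 mg/kg or discontinue if reduction has already occurred".
- **Grade 4:** "Discontinue treatment".

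Section 7.4.2 makes these thresholds operative: "Participants who require delay of BV should be re-evaluated frequently and BV dosing resumed when re-treatment criteria are met". It also sets 1.2 mg/kg as the lowest permitted dose.

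**The concern.** A restart rule should be at least as strict after a worse event. Here, for a participant on full dose, it is less strict. The same current state, Grade 2 neuropathy, means hold if Grade 2 was the peak and restart if the peak was Grade 3. The table also does not say whether the Grade 2 hold applies again once a participant is re-dosed while still at Grade 2.

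Peripheral neuropathy is one of the notable BV toxicities named in Section 3.3, and both arms receive BV. What is at stake is participant safety and consistent dosing across sites. No endpoint, estimate or error rate is affected.

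**Working it through.** The plan has no figure to reproduce here. The check compares the cells and looks for text that would reconcile them.

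**1. Two participants on 1.8 mg/kg with no earlier reduction**

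| | Participant A | Participant B |
|---|---|---|
| Peak neuropathy | Grade 2 | Grade 3 |
| Current neuropathy | Grade 2 | Grade 2 |
| Instruction, by triggering grade | Keep holding | May restart |
| Dose at restart | 1.2 mg/kg, once at Grade 1 or lower | 1.2 mg/kg, now |

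The restart dose is the same, so the only difference is when BV restarts, and it favors earlier dosing after the worse event.

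**2. Does the baseline wording explain it?** No. Section 6.2, criterion 2c, begins "Participants with neuropathy" and excludes Grade 2 or higher. Baseline is therefore Grade 0 or 1, and the operative limit in the Grade 3 cell is Grade 2.

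**3. Does other text explain it?** No. Sections 7.1.7 and 7.4.2 point back to the table. Footnote a covers the dose floor. The remaining footnotes cover electrolytes, infusion reactions, transfusion support and lymphopenia. Section 7.1.2 requires neurological toxicity to return to baseline before restarting, but its heading limits it to nivolumab. If it were read to cover BV, it would contradict the Grade 3 cell rather than explain it.

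**4. Comparison with the other rows**

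| Row | Action at Grade 2 | Restart ceiling after Grade 3 |
|---|---|---|
| Peripheral neuropathy | Hold | Grade 2 |
| Other non-hematologic | Continue, same dose | Grade 2 |
| Hematologic | Continue, same dose | Grade 2 |

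The ceiling is Grade 2 in 3 of 3 rows. In 2 of 3 it falls on a grade at which BV is given anyway, which is coherent. Only for neuropathy does it fall on a grade that itself triggers a hold. The hematologic Grade 3 cell, "Grade 2 or baseline, then resume treatment at the same dose level", matches the neuropathy cell until the restart dose. Carry-over between rows is plausible, but it is an inference.

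**5. Outer bound on BV doses given under the current revision.** Inputs:

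- Enrollment stopped on 17-Oct-2019.
- Section 7.1: "Participants should begin study treatment within 3 calendar days of randomization".
- Cycles last 21 days, with at most 16 BV cycles.
- Revised Protocol 01 is dated 08-Jan-2020.

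Assume the latest possible randomization and no delays:

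- Cycle 1: 17-Oct-2019 + 3 days = 20-Oct-2019.
- Cycle 16: 20-Oct-2019 + 15 × 21 = 315 days = 30-Aug-2020.
- Doses by 08-Jan-2020: 20-Oct, 10-Nov, 01-Dec and 22-Dec, so 4.
- Doses after it: 16 − 4 = 12.

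The last actual randomization date is not given, so the range is 0 to 12 on-schedule doses per participant. This shows only that the table could still have been in use after the revision. It does not measure impact, since an affected participant has had BV withheld and is not on schedule.

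**The case against.** The strongest case is that this is a narrow ambiguity with adequate protection.

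- **Already-reduced participants.** For someone already at 1.2 mg/kg, Grade 3 ends BV while Grade 2 only delays it, so the Grade 3 rule is the stricter one there. This stands, and it confines the inversion to participants not yet reduced.
- **Monitor contact.** Every affected restart is itself a reduction from 1.8 to 1.2 mg/kg, and Section 7.4 says "The BMS medical monitor should be contacted when any dose is reduced, regardless of the causality". Contact is therefore called for in every affected case. In addition, the modifications are described as recommended (7.4.2), delays beyond 3 weeks call for discussion with the monitor (7.1.7, 7.4.2), and the investigator can withhold or stop (7.1, 8.1). These points stand and lower the risk. They depend on someone noticing the problem, and they leave the threshold as it is.
- **Reading by current grade.** A participant back at Grade 2 could be placed under the Grade 2 hold. That reading is conservative, but it leaves the Grade 3 cell's Grade 2 ceiling with no effect. The row is defective on either reading.
- **Intent.** The neuropathy cell has its own dose and discontinuation clause, so it was at least partly tailored, and the documents do not state which threshold was meant. This stands, and it is why clinical confirmation is needed.
- **Other oddities in the table.** The hematologic Grade 3 cell cites the infusion-reaction footnote, and the lymphopenia footnote is cited nowhere. This weakens the row comparison as support. The finding rests on the two neuropathy cells, which are complete sentences with explicit thresholds.

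**Conclusion.** The concern holds. As written, the neuropathy row allows BV to restart at Grade 2 after a Grade 3 event, while a Grade 2 event must fall to Grade 1 or lower first. The discrepancy is one CTCAE grade at the same restart dose.

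It applies only to participants with Grade 3 neuropathy, no earlier BV reduction, and improvement to exactly Grade 2. The documents give no neuropathy rate and no count still on BV, so the number affected among the 23 randomized cannot be stated and may be zero. The conclusion assumes the table is read by triggering grade; reading it by current grade changes the form of the defect without removing it.

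This should be fixed as a safety and dosing rule.

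**What to change.** In the Grade 3 peripheral neuropathy cell of Table 7.4.2-1, change the restart ceiling from Grade 2 to Grade 1, keeping the baseline alternative, the 1.2 mg/kg restart dose and the instruction to stop if the dose was already reduced. The sponsor's clinical team should confirm this threshold first.

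If the team does intend restart at Grade 2, add a sentence saying that the Grade 2 hold does not apply to a participant re-dosed at Grade 2 after a Grade 3 event.

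Either way, notify sites with participants still on BV. The cost is one table cell, or one added sentence, plus a site letter or amendment. The downside of the stricter threshold is somewhat longer BV delays after Grade 3 neuropathy.

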Participants may continue on nivolumab or BV alone if required to discontinue one of the study medications. It is recommended to consult with the medical monitor before discontinuing one of the study medications.

Participants should be carefully monitored for infusion reactions during study treatment administration. If an acute infusion reaction related to nivolumab is noted, participants should be managed according to [Section 7.1.5](#).

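### The hematologic row of the BV dose table appears to give two rules for Grade 4 neutropenia: stop, or continue and only consider stopping if it recurs (minor; check the source page first)

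*Protocol*

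**What the plan says.** Protocol Table 7.4.2-1 sets BV dose changes by type and grade of toxicity. In the hematologic row:

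- The Grade 3 cell tells the site to hold BV until recovery to Grade 2 or lower or to baseline, to resume at the same dose, and to think about growth factor for later cycles. It then adds: "If Grade 4 neutropenia recurs despite growth factor support, consider discontinuation".
- The Grade 4 cell reads, in full, "Discontinue treatment".
- Footnote *e* makes one hematologic exception: "Participants who develop Grade 3 or 4 lymphopenia may continue study treatment without dose delay".

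Two sections send the reader to this table. Section 7.1.7 states: "Brentuximab vedotin treatment should be permanently discontinued for reasons provided in" Table 7.4.2-1. Section 7.4.2 is softer: "The recommended dose modifications for BV treatment associated toxicity are provided in" that table.

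**The concern.** A recurrent Grade 4 neutropenia is a Grade 4 hematologic toxicity, so both cells apply to it. One orders a stop and the other leaves it to judgment. Two investigators facing the same event could act in opposite ways, each able to point to the table.

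The conflict also reaches the first episode. An event can recur on BV despite growth factor only if BV was continued after the first one, which the Grade 4 cell does not allow.

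This is a patient-management issue. BV is given in both arms for up to 16 cycles, and Section 5.1 lets enrolled participants stay on treatment after enrollment closed, so the table was still in use under Revised Protocol 01. There is one side effect on data. In the BV-alone arm, stopping BV ends study treatment, and Table 2-3 then ends protocol scans for a participant who has not progressed.

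**Working it through.** No arithmetic applies. The check sets the two cells side by side for each event and then looks for a tie-breaker elsewhere.

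**1. What each cell says**

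| Event on BV | Grade 4 cell | Grade 3 cell | Conflict? |
|---|---|---|---|
| First Grade 4 neutropenia | Stop | Implies dosing may go on with growth factor | Yes, by implication |
| Grade 4 neutropenia recurring despite growth factor | Stop | Weigh stopping | Yes, expressly |
| Grade 4 lymphopenia | Stop, but footnote *e* allows dosing to go on | Silent | Settled by footnote *e* |
| Other Grade 4 hematologic toxicity | Stop | Silent | No |

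If the Grade 4 cell is applied literally, BV ends at the first Grade 4 neutropenia and the recurrence sentence can never be used. If the recurrence sentence has a use, the Grade 4 cell cannot be literal for neutropenia. The two cannot both stand as worded.

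**2. Is discretion at Grade 4 expressed elsewhere in the table?** Yes. The non-hematologic Grade 4 cell expressly lets the investigator choose between resuming at the reduced dose and stopping. The hematologic Grade 4 cell has no such words.

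**3. Does another section decide?**

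- Section 7.1.7 leads back to the table.
- Section 7.4.2 softens both cells equally.
- Section 7.1.6 exempts Grade 4 neutropenia of 7 days or less, but its list opens with "Nivolumab treatment should be permanently discontinued for the following". It is a nivolumab rule.
- Section 7.1, for the combination arm, gives a contact: "It is recommended to consult with the medical monitor before discontinuing one of the study medications". It gives no rule.
- Section 9 sends immediate safety concerns in either arm to the sponsor, again with no rule.
- Section 8.1 requires a stop, in either arm, when the investigator judges that an adverse event or laboratory abnormality makes continuing contrary to the participant's best interest. This limits harm but does not choose between the cells.

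**4. How reliable is the table text?** The header has five columns, and all five cells of the hematologic row hold their own text. The footnote markers in the table body are:

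| Footnote | Times marked | Where |
|---|---|---|
| *a* | 2 | Neuropathy Grade 2; non-hematologic Grade 4 |
| *b* | 2 | Non-hematologic Grades 3 and 4 |
| *c* | 2 | Non-hematologic Grade 4; hematologic Grade 3 |
| *d* | 1 | Hematologic row label |
| *e* | 0 | None |

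Footnote *c* says "Treatment should be discontinued for participants who experience Grade 4 infusion-related reactions", which does not belong in a hematologic Grade 3 cell. The marker there is probably a misread *e*, so the row was not read perfectly.

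**The case against.** The strongest objection is that the conflict comes from reading the PDF and is not in the protocol. A Grade 4 sentence sits in a Grade 3 cell. Footnote *e*, which covers Grades 3 and 4, has no marker. In the row above, the parallel footnote *b* is marked in both the Grade 3 and the Grade 4 cells, whereas the hematologic Grade 4 cell carries no marker. Its text is also identical to the neuropathy Grade 4 entry. All this would fit a single cell spanning Grades 3 and 4. Counting five filled cells is weak rebuttal, because it relies on the text in doubt. This part of the objection stands as a reason for lower confidence. It does not dispose of the point, because a merged cell would not explain why the row also has its own stop instruction.

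The second objection is that the conflict is mild. Stopping BV complies with both cells. A sentence specific to neutropenia can be read as qualifying a general cell that footnote *e* already shows is not absolute. The table is presented as a recommendation, Section 8.1 protects the participant, and Section 9.4.4 requires hematology results to be reviewed before dosing. This stands as a limit on the hazard. It still does not tell a site whether continuing BV after Grade 4 neutropenia is within the protocol.

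**Conclusion.** On the text available, Table 7.4.2-1 gives two instructions for Grade 4 neutropenia on BV, and nothing else in the protocol settles which applies. It is wrong as written and minor, with low-to-medium confidence, subject to a check of the source page.

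The ceiling is the 23 randomized participants. The documents do not say how many were still on BV or had Grade 4 neutropenia, so no count is offered.

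A reader might infer more, and the documents do not support it:

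- *The protocol certainly contains this error.* The marker pattern leaves a merged cell possible.
- *Participants could be kept on BV unsafely.* Section 8.1 requires a stop on the investigator's judgment, and stopping never breaches the table.
- *Trial results are affected.* Section 10 plans no formal testing or inferential analysis. At most, the duration of descriptive follow-up changes for an individual participant.
- *The whole Grade 4 hematologic rule is contradictory.* Only neutropenia is; lymphopenia is settled by footnote *e*.

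**What to change.** First compare the row with the source page. If it reads as above, state one rule for Grade 4 neutropenia in the Grade 4 cell and remove the Grade 4 sentence from the Grade 3 cell. The documents do not show which rule was intended, so the clinical team must choose:

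- **(a) Stop BV at the first Grade 4 neutropenia.** Delete the recurrence sentence. This is a clarification only.
- **(b) Allow one recovery.** Withhold BV until Grade 2 or lower or baseline, resume with growth factor support, and discontinue if Grade 4 neutropenia recurs despite it. The stop at recurrence should be definite; an instruction merely to consider it would leave the same variation between investigators. Keep the unqualified stop for other Grade 4 hematologic toxicity except lymphopenia.

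Either way, change the Grade 3 marker from *c* to *e* if the source also shows *c*, and add *e* to the Grade 4 cell.

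The cost is one table row, with no new data or procedures. Option (b) relaxes the literal Grade 4 cell, so the sponsor must decide under Appendix 2 (Compliance with the Protocol and Protocol Revisions) whether an administrative letter is enough or an amendment with revised consent is needed.
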